	
 
9. Compare patient satisfaction scores 48 hours later 
 
a. Overall experience
 
b. Quality of sedation
 
c. Pain experienced during procedure
 
d. Pain after the procedure
 
e. Nausea after awakening
 
f. Vomiting after awakening
 
g. Dizziness after awakening
 
h. Recollection of scope insertion
 
i. Recollection of scope removal
 
j. Awake during the procedure
 
k. Could drive at discharge if permitted
 
l. Would work at discharge if permitted
 
m. Time spent sleeping in the 24 hours after the procedure
 
n. Time could have driven after the procedure
 
 
 
10. Compare patient tolerance to SuperNO2VA™EtCO2 compared to control (ie: nasal cannula at 10LPM)
 
11. Compare endoscopist satisfaction scores for 
 
a. Overall experience
 
b. Rating of sedation
 
 
 

	
 
b. Rating of sedation
 
c. Difficulty of patient to sedate
 
d. Quality of the procedure
 
e. Difficulty of intubation
 

	
 
12. Compare anesthesiologists satisfaction scores 
 
a. Overall experience
 
b. Rating of sedation
 
c. Difficulty of patient to sedate
 
 
 
13. Compare the incidence of cardiac complications
 

Inclusion Criteria	
 
Age 18 years of age or older
 
Patients undergoing upper endoscopic ultrasound
 
American Society of Anesthesiology (ASA) Physical Status I-III
 
BMI ≥35 kg/m^2 or documented Obstructive Sleep Apnea
 
Has provided written informed consent
 

Exclusion criteria	
 
Inpatient status
 
Active Congestive Heart Failure Exacerbation
 
Untreated ischemic heart disease
 

	
 
Acute exacerbation of respiratory disorders, including COPD and asthma
 
Emergent procedures
 
Pregnancy
 
Rrevious enrollment in this study
 

	
 
8. Inability to provide informed consent
 

	
 
9. Additional medical testing planned for the same day
 
10. History of allergic reaction to Propofol
 
11. Tracheostomy
 
12. Supra-glottic or sub-glottic tumor
 
13. Gastrointestinal tract obstruction or delayed transit (including delayed gastric emptying, gastric bezoar, achalasia, toxic megacolon).
 

Study Procedures	
Pretreatment Evaluation	N/A
On-Study Visits	N/A
Follow-up Visits	Patient will complete a mail-in survey after 48 hours.
End of Study Visit	N/A
Brief Analysis Plan	Based on the literature the incidence of hypoxemia (ie: oxygen saturation < 90% for > 15 seconds) in using supplemental oxygen with nasal cannula is as high 43%. (Patel et. al.) Thus we expect the complication rate of hypoxemia in the SuperNO 2 VA™EtCO2 group to be 13%, we need 62 patients per group (112 patients in total) to detect this expected difference with 80% power at 0.05 two-sided level of significance. To adjust for 10% missing rate, we need approximately 124 patients in total.

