### **10. SAMPLE SIZE DETERMINATION AND DATA ANALYSIS**

### 10.1. Sample Size Determination

Power analyses were performed for the three primary objectives, using a power level of 0.80 and an alpha

Protocol #: IU IRB# 1810997768 Date: 31AUG21 Page 13 of 17

level of 0.05. Based on the literature the incidence of hypoxemia (ie: oxygen saturation < 90% for > 15 seconds) in using supplemental oxygen with nasal cannula is as high 43%. (Patel et. al.) Thus we expect the complication rate of hypoxemia in the SuperNO2VA EtM group to be 13%, we need 62 patients per group (124 patients in total). This sample size will allow us to detect this expected difference with 80% power at 0.05 two sided level of significance. To adjust for 10% missing rate, we need approximately 124 patients in total.

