### 10.2. Randomization

A random number generator program will be used to assign sequential qualified study cases to control group (N = 62) or SuperNO2VATMEtCO2 group (N = 62) before collection of additional demographic information and before anesthetic and surgical care. After study group assignment, baseline data will be collected, including age, gender, height, weight, and BMI.

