### **Data Safety Monitoring**

Two gastroenterologists ([name] and [name]), who are not a part of the study, will review adverse events, serious adverse and protocol deviations at the Indiana University site. These events and deviations will also be reported to the IU IRB as required. They will review all serious adverse events within 24 hours of their occurrence. Once 62 participants have been randomized, an interim analysis will be completed to review efficacy of primary endpoint, adverse events, serious adverse and protocol deviations. A final safety review will be performed once all the subjects complete the study.

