1. SAMPLE SIZE DETERMINATION AND DATA ANALYSIS

1.1. Sample Size Determination

Power analyses were performed for the three primary objectives, using a power level of 0.80 and an alpha level of 0.05. Based on the literature the incidence of hypoxemia (ie: oxygen saturation < 90% for > 15 seconds) in using supplemental oxygen with nasal cannula is as high 43%. (Patel et. al.) Thus we expect the complication rate of hypoxemia in the SuperNO₂VA Et^M group to be 13%, we need 62 patients per group (124 patients in total). This sample size will allow us to detect this expected difference with 80% power at 0.05 two sided level of significance. To adjust for 10% missing rate, we need approximately 124 patients in total.

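### The stated sample size does not follow from 43% versus 13% at 80% power, and the totals given before and after the missing-data allowance contradict each other

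*Protocol*

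**What the plan says.** The inputs are the same in all three places (the Brief Analysis Plan row of the Protocol summary table, Protocol section 10.1 and SAP section 1.1). The control rate of hypoxemia "in using supplemental oxygen with nasal cannula is as high 43" percent, the device-group rate is 13%, the level is two-sided 0.05, power is 80%, and 10% of data are expected to be missing.

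The results differ:

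- **Protocol summary table:** "we need 62 patients per group (112 patients in total) to detect this expected difference with 80% power at 0.05 two-sided level of significance", rising to about 124 with the allowance.
- **Protocol section 10.1:** "we need 62 patients per group (124 patients in total"), then "This sample size will allow us to detect this expected difference with 80% power at 0.05 two sided level of significance", then "To adjust for 10% missing rate, we need approximately 124 patients in total".
- **SAP section 1.1:** the same text as Protocol section 10.1.

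Protocol section 10.1 and SAP section 1.1 also open with a wider claim: "Power analyses were performed for the three primary objectives, using a power level of 0.80 and an alpha level of 0.05". Only incidence rates follow.

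Elsewhere 124 is used consistently as the number randomised. Protocol section 10.2 will "assign sequential qualified study cases to control group (N = 62") with the same number on the device, and the Data Safety Monitoring text in Protocol section 12 says "Once 62 participants have been randomized, an interim analysis will be completed", which is half of 124. Those passages contain no error.

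**The concern.** Three faults can be seen before any modelling. The summary table pairs 62 per group with a total that belongs to 56 per group. Section 10.1 and the SAP apply a 10% allowance that leaves the total unchanged. And a difference as large as 43% versus 13% should not need about 60 per group for 80% power.

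What is at stake is the design justification. If 124 already includes the allowance, the evaluable target is about 112. If 62 per group is the evaluable target, 124 contains no allowance and about 138 would have to be enrolled. The reader also cannot tell which test or power the size was built on, or whether duration and severity played any part in it.

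**Working it through.** **Inputs.** p1 = 0.43, p2 = 0.13, two-sided alpha 0.05 (z = 1.960), power 80% (z = 0.842), missing 10%, all from the sample-size statements. Allocation is 1:1, from Protocol section 10.2. The sample-size text names no test. Fisher's exact test is mentioned in Protocol section 5.2 and logistic regression in section 10.3, so several standard methods were tried.

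**1. Trying to reproduce 56 or 62 per group.**

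Pooled formula, with mean rate 0.28:

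n = [z(alpha/2) × √(2 × 0.28 × 0.72) + z(power) × √(0.43 × 0.57 + 0.13 × 0.87)]² / 0.30²

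= [1.960 × √0.4032 + 0.842 × √0.3582]² / 0.09 = (1.2445 + 0.5037)² / 0.09 = 33.96, so **34**.

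Continuity-corrected:

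n' = (n/4) × [1 + √(1 + 4/(n × 0.30))]² = (33.96/4) × (1 + √1.3926)² = 40.35, so **41**.

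Fisher exact, by full enumeration of both binomials: power is 79.5% at 38 and 80.2% at 39 per group, so **39**.

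Unpooled variance gives 32 and the arcsine method 33. One-sided testing gives 27, or 33 with continuity correction. No variant at 80% power comes near 56 or 62.

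With 10% missing: 34/0.9 = 37.8 and 41/0.9 = 45.6, so 38 to 46 enrolled per group.

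**2. The totals.**

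- 2 × 62 = 124, and 112 = 2 × 56.
- 112/0.9 = 124.4, and 56/0.9 = 62.2.
- 124/0.9 = 137.8, and 124 × 0.9 = 111.6.

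So 112 evaluable inflates to about 124 randomised. If instead 124 is the evaluable number, the allowance takes it to about 138.

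**3. What power would give these sizes?** Same formulas, per group:

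| Power | Pooled | Continuity-corrected |
|---|---|---|
| 80% | 33.96 | 40.35 |
| 85% | 38.6 | 45.06 |
| 90% | 44.96 | 51.4 |
| 95% | 55.2 (56) | 61.7 (62) |

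Only 95% power returns 56 and 62, and it does so with two different formulas.

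**4. Do the three primary objectives explain it?** Dividing alpha by three for incidence at 80% power gives 45.5 (pooled) or 51.96 (continuity-corrected). Fisher reaches 79.0% at 49 and 80.3% at 50. The most this can require is 52 evaluable, or 52/0.9 = 57.8, so 58 enrolled per group. An alpha split on incidence does not produce the stated size.

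**5. What the trial has.** Exact power by enumeration at a single two-sided 0.05 test:

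| Evaluable per group | 43% vs 13%: Fisher | 43% vs 13%: chi-square | Device rate at which power against 43% is about 80% |
|---|---|---|---|
| 56 | 93.4% | 95.7% | 17.5% (Fisher) to 19% (chi-square) |
| 62 | 95.6% | 97.2% | 18.5% (Fisher) to 19.9% (chi-square) |

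**The case against.** The best reply is that little turns on this. The claim of 80% power is true as a minimum, incidence power is 93% to 97%, and no patient or planned analysis changes. That is correct, and it is why this is a repair to the justification and not a threat to the trial.

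The documents also lean towards one reading. All three statements end with 124 as the figure adjusted for missing data, and 112 inflates to 124. So 56 evaluable and 62 randomised per group is the likelier intention. This stands, but section 10.1 and the SAP state 62 per group before the allowance, and 56 does not follow from 80% power either.

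The match with 95% power is suggestive only. The plan allows crossover in both directions (Protocol section 5.4) and an intention-to-treat analysis. If 10% crossed each way and took on the other arm's rate (an assumption found nowhere in the documents), the rates would become 40% versus 16%, and 80% power would need 54 per group (pooled) or 62 (continuity-corrected). No such allowance is stated, so it does not explain the figure, but it shows that 95% power is not the only candidate.

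Finally, duration or severity might have set the size. Step 4 tests only an alpha split on incidence and cannot exclude this. With no inputs shown for either, the possibility cannot be checked.

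**Conclusion.** The point holds and should be fixed. The stated need of 62 (or 56) per group does not follow from 43% versus 13% at two-sided 0.05 and 80% power, which requires 34 to 41 evaluable per group. The summary table contradicts itself on the total, and section 10.1 and the SAP include an allowance with no effect.

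For incidence the trial is larger than its inputs require. That conclusion assumes the stated rates and one two-sided 0.05 test. It does not cover crossover, the interim look with its possible early stop, or multiplicity across three primary objectives. Whether 80% is a misprint for 95% cannot be settled from the documents.

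**What to change.** The sponsor should retrieve the calculation that was run (test, power, evaluable number per group) and make the Protocol summary table, Protocol section 10.1 and SAP section 1.1 agree, naming the test and keeping evaluable and randomised numbers apart.

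- If 56 per group was the evaluable number: write 56 per group (112) evaluable and 62 per group (124) randomised in all three places.
- If 62 per group was the evaluable number: remove the total of 112, say that 124 contains no allowance, and give the power with about 56 evaluable per group.

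Under either text, state that about 112 evaluable patients (56 per group) give about 93% (Fisher) to 96% (chi-square) power for 43% versus 13%, or 80% power for 43% versus about 17.5% to 19%, and that 62 evaluable per group give about 96% to 97%. Say that these figures are for incidence at one two-sided 0.05 test. Then either show the inputs for duration and severity or state that only incidence was powered.

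The cost is wording in three places after one check. On the incidence calculation 124 randomised (62 per group) stays. Enrolment would come into question only if the check showed that duration or severity required 62 evaluable per group.

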# 1. OBJECTIVES

# **Primary Objective**

The primary objective of the study is to prospectively and randomly compare the incidence, duration, and severity of oxygen desaturation between a nasal mask with nasal positive airway pressure (PAP) versus standard care (nasal cannula) during propofol-based sedation for endoscopic ultrasound in an ambulatory surgical center (ASC) in patients considered high risk for hypoxia (ie: BMI ≥35 kg/m^2 or documented Obstructive Sleep Apnea.

# **Endpoints of Interest**

- 1. Compare the amount of propofol administered during induction and total dose administered for procedure
- 2. Compare Modified Observer's Assessment of Alertness/Sedation Scale (MOAAS) scores immediately prior to endoscopic intubation and during the procedure

Protocol #: IU IRB# 1810997768 Date: 31AUG21 Page 5 of 17

- 3. Compare the length of time from induction to endoscopic insertion
- 4. Compare the incidence and duration of procedural interruptions (ie: number of times and length of time the endoscope is removed from the patient)
- 5. Compare the incidence, duration, and reason for airway maneuvers
- 6. Compare the length of time for the procedure (ie: length of time from procedure start to procedure end)
- 7. Compare recovery times
- 8. Compare patient satisfaction scores (visual analog scale (VAS)) immediately after procedure
- 9. Compare patient satisfaction scores 48 hours later
- 10. Compare patient tolerance to SuperNO2VA EtCO2 compared to control (ie: nasal cannula at 10LPM)
- 11. Compare endoscopist satisfaction scores for
- 12. Compare anesthesiologists satisfaction scores
- 13. Compare the incidence of cardiac complications

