### 3.2. Inclusion and Exclusion Criteria

#### a) Inclusion Criteria:

- 1. Age 18 years of age or older
- 2. Patients undergoing upper endoscopic ultrasound
- 3. American Society of Anesthesiology (ASA) Physical Status I-III
- 4. BMI  $\geq$  35 kg/m^2 or documented Obstructive Sleep Apnea
- 5. Has provided written informed consent

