### 5.2 Methods:

This study involves the oxygenation, continuous positive airway pressure, and ventilation of a subject via nasal mask and oxygenation via a closed facemask. The interventions directly related to this study are that of supplement oxygen, bag-mask ventilation, and continuous nasal CPAP intra-operatively and in the Post Anesthesia Care Unit.

Patients will be randomized in groups of ten to one of two groups using a random number table. Group A: Standard care with a nasal cannula. Group B: SuperNO2VA™EtCO2.

For each anesthetic case, a preoperative history and physical and intraoperative record will be documented (table 1).

Table 1: General Patient characteristics	
Age (years)	
Gender (M/F)	
Height (cm)	
Weight (kg)	
BMI (kg/m  )	
ASA classification (I-III)	
Diagnosed OSA on home CPAP	
Diagnosed OSA not on home CPAP	
STOP-BANG Score	
Patient Co-morbidities*	

\*Co-morbidities include any history of: hypertension, diabetes, coronary disease, valvular disease, arrhythmia, cerebrovascular disease, active cancer, tobacco use, pulmonary disease, renal disease, liver disease.

Once in the endoscopy suite, the patients will have continuous monitoring of heart rate, end tidal CO2 (EtCO2), O2 saturation, and every 2-minute BP monitoring. Patients randomized to group A, the anesthesia provider will supply oxygen via nasal cannula at 10LPM. Patients randomized to group B, the anesthesia provider will attach the SuperNO2VAM EtCO2's circuit port to the hyperinflation bag with the oxygen flow rate to 10 L/min, and the APL valve completely closed. Initial dosing bolus 0.5-1.0 mg/kg actual body weight of Propofol will be administered for sedation and MOAA/S scores will be assessed. Nursing or the research assistant will then record the patient's MOAA/S score. If the patient's MOAA/S score of <4 reached. Once a MOAA/S score of <4 is reached the endoscopist will perform endoscopic intubation and the goal will be to maintain a MOAA/S score of <4 until the procedure is over. If the patient's MOAA/S score  $\geq 4$ , additional 10 – 40mg bolus of propofol will be administered every 30–90 seconds until the

Protocol #: IU IRB# 1810997768 Date: 31AUG21 Page 9 of 17

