MOAA/S is <4. The measurements that will be made are the following: the incidence, severity, and time of oxygen desaturation, number of airway maneuvers performed, duration of airway maneuvers, reason for performing the airway maneuver, the onset time of administration of sedation, the duration of the procedure, the total dosage of the medication, vital signs - blood pressure, heart rate, and oxygen saturation, the time to full recovery, and patient cooperation. Nursing or the research assistant will document their patient's depth of sedation, cooperation with procedure, and safety. Patients will recover in the endoscopy suite. The patients will have continuous monitoring of heart rate, end tidal CO2 (EtCO2), O2 saturation, and every 5-minute BP monitoring and MOAAS Score. The time to discharge will be obtained for each patient. Patients will also complete a satisfaction and pain questionnaire before they are discharged. Patients will also be asked to complete another questionnaire within 48 hours concerning their satisfaction and their subjective degree of impairment due to the sedation either with a paper form and self-addressed envelope or electronically sent via e mail. If the patients do not complete their questionnaire, someone will contact them by telephone to collect the data. A statistician using student T-test, Fishers exact test, and other statistical methods they deem appropriate will analyze the collected data.

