#### **10.3.** Planned Statistical Analysis

Although randomization into treatment groups should minimize differences between the groups, basic bivariate analyses will be performed to determine if there are any clinical or demographic differences, using the data collected in table 1. Logistic regression models will be performed to determine if there are significant differences between the groups for both incidence and severity. Student's t-tests will be performed to determine if there is a significant difference between groups for duration, with Wilcoxon non-parametric tests being performed if the data are non-linear. If significant differences in clinical or demographics characteristics were found, multivariable models will be performed to adjust for these possible confounding variables using logistic regression and ANCOVA models (with GEE models being used to model non-linear data with the appropriate exponential family distribution). All analytic assumptions will be verified and all analyses performed with SAS v9.4, SAS Institute, Cary, NC), analyzing the data as both per-protocol and intention-to-treat.

A Data Safety and Monitoring Board (DSMB) will be convened once half the necessary study population has been enrolled, to discuss the current status of primary endpoints and adverse events, all of which will be tabulated throughout the study. If effect sizes are larger than originally planned and there is a statistically significant decrease in the primary event at this halfway mark, the study will end at this time.

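### The propofol comparison makes no planned use of recorded body weight, which gives up precision, chiefly for the induction amount

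*Protocol*

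**What the plan says.** The Protocol lists the outcome in its Summary Table (secondary outcome 1) and under Endpoints of Interest (item 1): "Compare the amount of propofol administered during induction and total dose administered for procedure". Section 5.2 lists "the total dosage of the medication" among the measurements. None of these places gives a unit, a per-kilogram or per-time scale, or a covariate.

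Section 5.2 sets two kinds of dose. The first follows body size: "Initial dosing bolus 0.5-1.0 mg/kg actual body weight of Propofol will be administered for sedation". The later ones do not: if the MOAA/S score is still 4 or more, an "additional 10 – 40mg bolus of propofol will be administered every 30–90 seconds until the" score falls below 4.

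Patients enter with a BMI of at least 35 "or documented Obstructive Sleep Apnea", so the second route has no BMI limit. Weight is recorded in Table 1.

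On analysis, section 5.2 says: "A statistician using student T-test, Fishers exact test, and other statistical methods they deem appropriate will analyze the collected data". Protocol 10.3 and SAP 1.3 name methods for incidence, severity and duration of desaturation, and then add: "If significant differences in clinical or demographics characteristics were found, multivariable models will be performed to adjust for these possible confounding variables". Propofol is not mentioned there.

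**The concern.** Weight is known before treatment, is already recorded, and by the dosing rule predicts at least part of the dose. Leaving it out of the comparison leaves avoidable variance in the estimate. The rule for adding covariates does not repair this, because it acts only when weight happens to be significantly unbalanced. The value of adjusting comes from how strongly weight predicts dose, and that is the same whether or not the arms are balanced.

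What is at stake is the power and interval width of one secondary outcome. It is a useful one, because readers will want to know whether the arms received similar amounts of sedative when they interpret the desaturation result. With no method fixed, raw mg, mg/kg, mg/kg per hour and a weight-adjusted model all also remain open choices after the data are seen.

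**Working it through.** **Plan's own figure.** There is none to reproduce. No power, SD or target difference is stated for propofol, and no spread is given for weight or dose.

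**Inputs from the documents.** First bolus 0.5-1.0 mg/kg actual weight; later boluses a fixed 10-40 mg (Protocol 5.2); 62 patients per arm (10.1, 10.2). The two-sided 0.05 level and 80% power are borrowed from 10.1, where they serve the hypoxemia rate.

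**Assumptions.** Mean weight 110 kg; weight CV 0.20 or 0.30; first-bolus rate b uniform on 0.5-1.0 mg/kg (mean 0.75, variance 0.5²/12 = 0.0208); later boluses sum to T with mean 20, 60, 150 or 300 mg, SD half the mean, unrelated to weight.

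**Step 1: the dosing rule alone.** At an illustrative 60 kg the first bolus is 30-60 mg; at 150 kg it is 75-150 mg. The ranges do not overlap. This compares two chosen patients, not the two arms.

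**Step 2: share of variance due to weight.** Dose D = bW + T, so

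Var(D) = E(b²)·E(W²) − (0.75 × 110)² + Var(T), and R² = (0.75 × SD of W)² / Var(D).

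For weight CV 0.20 (SD 22 kg) and T averaging 20 mg:
- E(b²) = 0.5625 + 0.0208 = 0.5833; E(W²) = 110² × 1.04 = 12,584
- Var(D) = 7,340.7 − 6,806.3 + 100 = 634.4
- R² = 272.25 / 634.4 = 0.43
- raw CV = √634.4 / 102.5 = 0.246; weight-adjusted CV = 0.246 × √(1 − 0.43) = 0.186

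The detectable difference, as a share of the mean, is (1.96 + 0.84) × CV × √(2/62) = 0.503 × CV. Simulation of the same scheme gives these CVs and R²; the closed form agrees to rounding.

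| Weight CV | Mean later boluses (mg) | R² | CV raw mg | CV mg, weight-adjusted | CV mg/kg | Detectable, raw | Detectable, adjusted |
|---|---|---|---|---|---|---|---|
| 0.20 | 20 | 43% | 0.246 | 0.186 | 0.189 | 12.4% | 9.4% |
| 0.30 | 20 | 62% | 0.306 | 0.189 | 0.198 | 15.4% | 9.5% |
| 0.20 | 60 | 19% | 0.266 | 0.240 | 0.260 | 13.4% | 12.1% |
| 0.30 | 60 | 34% | 0.296 | 0.240 | 0.287 | 14.9% | 12.1% |
| 0.20 | 150 | 4% | 0.338 | 0.330 | 0.365 | 17.0% | 16.6% |
| 0.30 | 150 | 10% | 0.347 | 0.330 | 0.404 | 17.5% | 16.6% |
| 0.20 | 300 | 1% | 0.396 | 0.394 | 0.435 | 19.9% | 19.8% |
| 0.30 | 300 | 3% | 0.399 | 0.394 | 0.484 | 20.1% | 19.8% |

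The upper rows resemble an induction amount with few later boluses; the lower rows resemble a total dose made up mostly of fixed boluses. Weight adjustment never does worse than raw mg. Dividing by weight does worse in the lower rows.

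**Step 3: an upper bound.** If the whole dose scaled with weight, CV(raw)² = CVr² + CVw² + CVr²·CVw², where CVr is the CV of mg/kg. With CVr 0.30 and CVw 0.20 this is 0.09 + 0.04 + 0.0036 = 0.1336, which is 1.48 times 0.09. Power for a 20% difference is then 86% raw against 96% once weight is removed. Over CVr 0.30-0.50 and CVw 0.15-0.30 the variance ratio runs from 1.11 to 2.09. The protocol's fixed later boluses keep the real figure below this bound unless titration makes them track weight too.

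**Step 4: the conditional rule.** Under randomization, a 0.05-level baseline test of weight (level assumed) is significant in about 5% of trials. The threshold is 1.96 × CVw × √(2/62): 5.3% of mean weight at CV 0.15, 7.0% at 0.20, 10.6% at 0.30. In the other 95% or so of trials, weight is not used at all.

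**The case against.** **This is under-specification, not a commitment to raw mg.** That is fair. No unit is stated, the first bolus is itself expressed per kilogram, and section 5.2 leaves the statistician free to choose. But an open choice does not secure the gain, and it leaves the choice of scale to be made with the data in view.

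**A reader might infer that body size biases the comparison.** The documents do not support this. Weight precedes randomization, so it contributes noise and chance imbalance that the standard error already reflects.

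**A reader might also infer that mg/kg, or mg/kg per hour, should be the definition.** The dosing rule does not support that. Only the first bolus is per kilogram, so dividing a total dose by weight can raise its CV, as the table shows. Procedure length bears on the total but not on the induction amount. It follows randomization, is compared in its own right ("Compare the length of time for the procedure"), and may respond to the device, since an interruption is defined as scope removal for a respiratory complication. An hourly rate therefore answers a different question: an arm with longer, interrupted procedures could show a lower rate while receiving more drug. Total drug received is a legitimate outcome.

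**Wide weight variation is inferred.** This stands. It follows plausibly from the two entry routes, but no weight distribution is given. Titration to MOAA/S could also weaken or strengthen the link between weight and dose.

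**Conclusion.** The point holds as a loss of precision in one of 13 secondary outcomes. The plan does not use a recorded baseline variable that its own dosing rule ties to the first bolus, and the significance-triggered adjustment does not make up for it.

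Under the stated assumptions, adjustment lowers the detectable difference from about 12-15% to about 9-10% of the mean when later boluses average 20 mg, and changes it by less than one percentage point when they average 150 mg or more. All of this rests on assumed CVs, an assumed mean weight and later boluses unrelated to weight. No bias is shown, and the primary outcome is unaffected. It is a free improvement, not a flaw that threatens the trial.

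**What to change.** In the Summary Table (secondary outcome 1), Endpoints of Interest (item 1), Protocol 10.3 and SAP 1.3:

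- State the outcome in mg. Induction amount runs from first bolus to first scope insertion; total amount runs from first bolus to last scope removal. These windows fit the time definitions already in Protocol 5.3.
- Compare each amount between arms by ANCOVA with baseline weight as a covariate in all patients, whatever the baseline tests show.
- Report mg/kg and mg/kg per hour as supportive summaries only, noting that procedure length is post-randomization and may be affected by the device.

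The cost is wording and one model term. Weight, dose and procedure timing are already among the planned measurements, and neither the sample size nor patient care changes.
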